11.0 Data Quality Assurance

Computer logic and manual checks will be created to identify items such as inconsistent study dates. Any necessary corrections will be made to the eCRF.

12.0 Use of Information

All information concerning adalimumab and AbbVie operations, such as AbbVie patent applications, formulas, manufacturing processes, basic scientific data, or formulation

information, supplied by AbbVie and not previously published is considered confidential information.

The information developed during the conduct of this clinical study is also considered confidential and will be used by AbbVie in connection with the development of adalimumab. This information may be disclosed as deemed necessary by AbbVie to other clinical investigators, other pharmaceutical companies, to the FDA and to other governmental agencies. To allow for the use of the information derived from this clinical study and to ensure complete and thorough analysis, the investigator is obligated to provide AbbVie with complete test results and all data developed in this study and to provide direct access to source data/documents for trial-related monitoring, audits, IEC/IRB review, and regulatory inspection.

This confidential information shall remain the sole property of AbbVie, shall not be disclosed to others without the written consent of AbbVie, and shall not be used except in the performance of this study.

The investigator will maintain a confidential subject identification code list of all subjects enrolled in the study (by name and subject number). This list will be maintained at the site and will not be retrieved by AbbVie.

13.0 Completion of the Study

The end-of-study is defined as the date of the last subject's last visit or the actual date of follow-up contact, whichever is later.

The investigator will conduct the study in compliance with the protocol and complete the study within the timeframe specified in the contract between the investigator and AbbVie. Continuation of this study beyond this date must be mutually agreed upon in writing by both the investigator and AbbVie. The investigator will provide a final report to the IEC/IRB following conclusion of the study, and will forward a copy of this report to AbbVie or their representative.

The investigator must retain any records related to the study according to local requirements. If the investigator is not able to retain the records, he/she must notify AbbVie to arrange alternative archiving options.

AbbVie will select the signatory investigator from the investigators who participate in the study. Selection criteria for this investigator will include level of participation as well as significant knowledge of the clinical research, investigational drug and study protocol. The signatory investigator for the study will review and sign the final study report in accordance with the European Agency for the Evaluation of Medicinal Products (EMEA) Guidance on Investigator's Signature for Study Reports.

Appendix A. Responsibilities of the Clinical Investigator

Clinical research studies sponsored by AbbVie are subject to the Good Clinical Practices (GCP) and local regulations and guidelines governing the study at the site location. In signing the Investigator Agreement in Section 14.0 of this protocol, the investigator is agreeing to the following:

1. Conducting the study in accordance with the relevant, current protocol, making changes in a protocol only after notifying AbbVie, except when necessary to protect the safety, rights or welfare of subjects.
2. Personally conducting or supervising the described investigation(s).
3. Informing all subjects, or persons used as controls, that the drugs are being used for investigational purposes and complying with the requirements relating to informed consent and ethics committees (e.g., independent ethics committee [IEC] or institutional review board [IRB]) review and approval of the protocol and amendments.
4. Reporting adverse experiences that occur in the course of the investigation(s) to AbbVie and the site director.
5. Reading the information in the Investigator's Brochure/safety material provided, including the instructions for use and the potential risks and side effects of the investigational product(s).
6. Informing all associates, colleagues, and employees assisting in the conduct of the study about their obligations in meeting the above commitments.
7. Maintaining adequate and accurate records of the conduct of the study, making those records available for inspection by representatives of AbbVie and/or the appropriate regulatory agency, and retaining all study-related documents until notification from AbbVie.
8. Maintaining records demonstrating that an ethics committee reviewed and approved the initial clinical investigation and all amendments.

9. Reporting promptly, all changes in the research activity and all unanticipated problems involving risks to human subjects or others, to the appropriate individuals (e.g., coordinating investigator, institution director) and/or directly to the ethics committees and AbbVie.
10. Following the protocol and not make any changes in the research without ethics committee approval, except where necessary to eliminate apparent immediate hazards to human subjects.

Adalimumab
M14-347 Protocol Amendment 2
EudraCT 2013-004034-15

Appendix D. Sample EQ-5D Questionnaires

[figure not shown]
Adalimumab
M14-347 Protocol Amendment 2
EudraCT 2013-004034-15

Adalimumab
M14-347 Protocol Amendment 2
EudraCT 2013-004034-15

[figure not shown]
**Appendix E. Sample Quality of Life in Inflammatory Bowel Disease
Questionnaire (IBDQ)**

Adalimumab
M14-347 Protocol Amendment 2
EudraCT 2013-004034-15

QUALITY OF LIFE IN INFLAMMATORY BOWEL DISEASE QUESTIONNAIRE (IBDQ)

A large, solid black rectangular box that completely obscures the content of the Quality of Life in Inflammatory Bowel Disease Questionnaire (IBDQ) section. It is positioned below the section header and spans most of the page width.

[figure not shown]

Adalimumab
M14-347 Protocol Amendment 2
EudraCT 2013-004034-15

[figure not shown]

Adalimumab
M14-347 Protocol Amendment 2
EudraCT 2013-004034-15

Adalimumab
M14-347 Protocol Amendment 2
EudraCT 2013-004034-15

Adalimumab
M14-347 Protocol Amendment 2
EudraCT 2013-004034-15

[figure not shown]

Adalimumab
M14-347 Protocol Amendment 2
EudraCT 2013-004034-15

Adalimumab
M14-347 Protocol Amendment 2
EudraCT 2013-004034-15

Adalimumab
M14-347 Protocol Amendment 2
EudraCT 2013-004034-15

Adalimumab
M14-347 Protocol Amendment 2
EudraCT 2013-004034-15

Adalimumab
M14-347 Protocol Amendment 2
EudraCT 2013-004034-15

Appendix F. Abdominal Pain Rating Scale

Adalimumab
M14-347 Protocol Amendment 2
EudraCT 2013-004034-15

Appendix G. Injection Instructions – Sample Pre-Filled Syringe

Subject Instructions

0.8 mL dose

(Administered as a single dose-pre-filled syringe)

Protocol M14-347

Table of Contents

Dosing Schedule

General Information and Supplies

Injection Procedures

Study Drug Dosing Schedule

Subject Number: _____

You will require subcutaneous injections throughout the study. Depending how active your Crohn's disease is, your dosing schedule may change. You will receive 1 injection at the clinic at your Baseline Visit (the first visit to receive the study medication for this study).

If your Crohn's disease is under control, then you will take 1 injection every other week. You will receive the following number of injections during the study:

- Weeks 2, 4, 6, 10, 12, 14, 18, 20, 22, 26, 28, 30, 34, 36 and 38 you will administer 1 injection at home.
- At Weeks 8, 16, 24 and 32 you will receive 1 injection at the clinic.

If your Crohn's disease worsens, then your study physician may need to change your dosing schedule and you could begin taking 1 injection every week.

If you feel better at a future visit while taking 1 injection every week, then you may go back to taking 1 injection every other week.

Please return all used and unused syringes and empty boxes to the clinic on your next visit. Used syringes should be placed in the special sharps container provided. All unused syringes should be returned in the original box.

If an injection is missed or something occurs where the full dose cannot be injected, contact your study center immediately for further instructions. Please record any missed doses on your subject dosing diary.

Remember to complete your dosing diary after each injection and to call the doctor's office if you are having problems administering your study medication.

General Information

- Pre-filled syringes will be labeled "Adalimumab."
- Store all adalimumab pre-filled syringes in your refrigerator NOT in the freezer. Should the syringes accidentally become frozen, call your study doctor's office.
- Study medication should be taken at about the same time of day, on the same day of the week as directed by your study doctor.
- **USE A NEW SYRINGE EVERY INJECTION DAY.** There may be medication left in the syringe. **DO NOT RE-USE.**
- Save all study medications. ***Pre-filled syringes (used and unused) & empty boxes must be returned to the study center at each visit.*** Used syringes will be disposed of in a sharps container provided to you.
- Call your doctor IMMEDIATELY if you experience any itching, hives, shortness of breath, or any symptom that has you concerned. If you are unable to reach your doctor or if you experience life-threatening symptoms call _____, or proceed to your nearest emergency room.

Injection Procedures (PFS)

1. Setting up for an injection

- Find a clean flat surface.
- Do not use if the seals on the carton are broken or missing. Contact your study doctor's office if the seals are broken.
- Take one kit with the prefilled syringe(s) of adalimumab from the refrigerator. Do not use a prefilled syringe that has been frozen or if it has been left in direct sunlight.
- Return any unused syringe(s) to the refrigerator.

You will need the following items for each dose:

- study medication in pre-filled syringe(s)

- alcohol prep(s)
- cotton ball or gauze pad(s)

[figure not shown]

If you do not have all of the items you need to give yourself an injection, call your study physician. Use only the items provided in the box your adalimumab comes in.

- Make sure the liquid in the prefilled syringe is clear and colorless. Do not use a prefilled syringe if the liquid is cloudy or discolored or has flakes or particles in it.
- Have a special sharps (puncture proof) container nearby for disposing of used needles and syringes.

For your protection, it is important that you follow these instructions.

2. Choosing and preparing an injection site

- Wash your hands well.
- Choose a site on the front of your thighs or your stomach area (abdomen). If you choose your abdomen, you should avoid the area 2 inches around your belly button (navel).
- Choose a different site each time you give yourself an injection. Each new injection should be given at least one inch from a site you used before. Never inject into areas where the skin is tender, bruised, red or hard or where you have scars or stretch marks.
- If you have psoriasis, you should try not to inject directly into any raised, thick, red or scaly skin patches or lesions.
- You may find it helpful to keep notes on the location of your injection sites.
- Wipe the site where adalimumab is to be injected with an alcohol prep (swab), using a circular motion. Do not touch this area again until you are ready to inject.

3. How to prepare your adalimumab dose for injection with a Prefilled Syringe

- Hold the syringe upright with the needle facing down. Check to make sure that the amount of liquid in the syringe is the same or close to the 0.8 mL line for the 40 mg prefilled syringe. The top of the liquid may be curved. If the syringe does not have the correct amount of liquid, do not use that syringe. Call your study doctor.
- Remove the needle cover taking care not to touch the needle with your fingers or allow it to touch any surface.
- Turn the syringe so the needle is facing up and slowly push the plunger in to push the air in the syringe out through the needle. If a small drop of liquid comes out of the needle that is okay.
- Do not shake the syringe.

4. Injecting Adalimumab

- With your other hand, gently squeeze an area of the cleaned area of skin and hold it firmly.

- You will inject into this raised area of skin. Hold the syringe like a pencil at about a 45° angle (see picture) to the skin.
- With a quick, short, "dart-like" motion, push the needle into the skin.
- After the needle is in, let go of the skin. Pull back slightly on the plunger. If blood appears in the syringe it means that you have entered a blood vessel. Do not inject adalimumab. Pull the needle out of the skin and repeat the steps to choose and clean a new injection site. Do not use the same syringe. Dispose of it in your special sharps container. If no blood appears, slowly push the plunger all the way in until all of the adalimumab is injected.
- When the syringe is empty, remove the needle from the skin keeping it at the same angle it was when it was pushed into the skin.
- Press a cotton ball or gauze pad over the injection site and hold it for 10 seconds. Do not rub the injection site. You may have slight bleeding. This is normal.
- Dispose of the syringe right away into your special sharps container.

Appendix H. Crohn's Disease Activity Index (CDAI)

		Factor	Subtotal
1. Number of liquid or very soft stools (Record the frequency per day)		×	2
2. Abdominal pain rating: 0 = none, 1 = mild, 2 = moderate, 3 = severe	____ + ____ + ____ + ____ + ____ + ____ + ____ = ____ Days: 1 2 3 4 5 6 7 Sum	×	5
3. General well-being: 0 = generally well, 1 = slightly underpar, 2 = poor, 3 = very poor, 4 = terrible	____ + ____ + ____ + ____ + ____ + ____ + ____ = ____ Days: 1 2 3 4 5 6 7 Sum	×	7
4. Number of 6 listed categories the subject now has Check all items that apply:  Arthritis/arthralgia  Iritis/uveitis  Erythema nodosum/pyoderma gangrenosum/aphthous stomatitis  Fissure, abscess and/or anal fistula (draining/non-draining)  Other cutaneous fistula (draining/non-draining)  Fistula  Fever over 100°F (37.8°C) during past week	_____ _____ Record "0" if no categories checked	×	20
5. Taking Lomotil/Imodium/ Loperamide/opiates for diarrhea 0 = no, 1 = yes	_____	×	30
6. Abdominal mass 0 = none, 2 = questionable, 5 = defined	_____	×	10
7. Hematocrit: _____.____	Male: (47 – hematocrit) = Female: (42 – hematocrit) = Subtotal If hematocrit > normal, enter "0"	×	6
8. Body weight: _____.____(kg) Standard weight: _____.____(kg)	100 × [1 – (Body wt/Standard wt)] = Percent below standard weight: _____ If body wt > std. wt, enter "0"	×	1
			Total

Appendix I. Standard Weights

Standard Height and Weight Tables – Use to Calculate CDAI Score		
Actual Height cm (Inches)	Standard Weight (Men) kg (Pounds)	Standard Weight (Women) kg (Pounds)
121.9 (48.0)		40.8 (89.9)
123.2 (48.5)		41.3 (91.0)
124.5 (49.0)		41.8 (92.1)
125.7 (49.5)		42.3 (93.3)
127.0 (50.0)		42.8 (94.4)
128.3 (50.5)		43.4 (95.6)
129.5 (51.0)		43.9 (96.8)
130.8 (51.5)		44.4 (98.0)
132.1 (52.0)	55.5 (122.4)	45.0 (99.2)
133.4 (52.5)	55.7 (122.7)	45.5 (100.4)
134.6 (53.0)	55.8 (123.1)	46.1 (101.6)
135.9 (53.5)	56.0 (123.5)	46.6 (102.8)
137.2 (54.0)	56.2 (123.9)	47.2 (104.1)
138.4 (54.5)	56.4 (124.4)	47.8 (105.3)
139.7 (55.0)	56.7 (124.9)	48.3 (106.6)
141.0 (55.5)	56.9 (125.5)	48.9 (107.9)
142.2 (56.0)	57.2 (126.1)	49.5 (109.1)
143.5 (56.5)	57.4 (126.7)	50.1 (110.4)
144.8 (57.0)	57.7 (127.3)	50.7 (111.7)
146.1 (57.5)	58.1 (128.0)	51.3 (113.0)
147.3 (58.0)	58.4 (128.7)	52.2 (115.0)
148.6 (58.5)	58.7 (129.5)	52.6 (116.0)
149.9 (59.0)	59.1 (130.3)	53.1 (117.0)
151.1 (59.5)	59.5 (131.1)	53.6 (118.3)
152.4 (60.0)	59.9 (132.0)	54.2 (119.5)
153.7 (60.5)	60.3 (132.9)	54.8 (120.8)
154.9 (61.0)	60.7 (133.8)	55.3 (122.0)
156.2 (61.5)	61.1 (134.8)	56.0 (123.5)
157.5 (62.0)	61.7 (136.0)	56.7 (125.0)

Standard Height and Weight Tables – Use to Calculate CDAI Score		
Actual Height cm (Inches)	Standard Weight (Men) kg (Pounds)	Standard Weight (Women) kg (Pounds)
158.8 (62.5)	62.1 (137.0)	57.4 (126.5)
160.0 (63.0)	62.6 (138.0)	58.0 (128.0)
161.3 (63.5)	63.0 (139.0)	58.7 (129.5)
162.6 (64.0)	63.5 (140.0)	59.4 (131.0)
163.8 (64.5)	64.1 (141.3)	60.1 (132.5)
165.1 (65.0)	64.6 (142.5)	60.8 (134.0)
166.4 (65.5)	65.2 (143.8)	61.4 (135.5)
167.6 (66.0)	65.8 (145.0)	62.1 (137.0)
168.9 (66.5)	66.4 (146.5)	62.8 (138.5)
170.2 (67.0)	67.1 (148.0)	63.5 (140.0)
171.5 (67.5)	67.8 (149.5)	64.2 (141.5)
172.7 (68.0)	68.5 (151.0)	64.9 (143.0)
174.0 (68.5)	69.2 (152.5)	65.5 (144.5)
175.3 (69.0)	69.8 (154.0)	66.2 (146.0)
176.5 (69.5)	70.5 (155.5)	66.9 (147.5)
177.8 (70.0)	71.2 (157.0)	67.6 (149.0)
179.1 (70.5)	71.9 (158.5)	68.3 (150.5)
180.3 (71.0)	72.6 (160.0)	68.9 (152.0)
181.6 (71.5)	73.4 (161.8)	69.6 (153.5)
182.9 (72.0)	74.1 (163.5)	70.3 (155.0)
184.2 (72.5)	75.0 (165.3)	71.2 (156.9)
185.4 (73.0)	75.7 (167.0)	71.9 (158.5)
186.7 (73.5)	76.6 (169.0)	72.6 (160.2)
188.0 (74.0)	77.5 (171.0)	73.4 (161.8)
189.2 (74.5)	78.4 (172.8)	74.1 (163.4)
190.5 (75.0)	79.1 (174.5)	74.9 (165.1)
191.8 (75.5)	80.2 (176.8)	75.6 (166.8)
193.0 (76.0)	81.2 (179.0)	71.2 (156.9)
194.3 (76.5)	82.0 (180.8)	77.2 (170.1)
195.6 (77.0)	82.9 (182.9)	77.9 (171.8)
196.9 (77.5)	83.9 (185.0)	78.7 (173.5)

Standard Height and Weight Tables – Use to Calculate CDAI Score		
Actual Height cm (Inches)	Standard Weight (Men) kg (Pounds)	Standard Weight (Women) kg (Pounds)
198.1 (78.0)	84.9 (187.2)	79.5 (175.2)
199.4 (78.5)	85.9 (189.4)	80.3 (177.0)
200.7 (79.0)	86.9 (191.6)	81.0 (178.7)
201.9 (79.5)	87.9 (193.9)	81.8 (180.5)
203.2 (80.0)	89.0 (196.2)	82.6 (182.2)
204.5 (80.5)	90.0 (198.6)	*Height in shoes with one inch heels
205.7 (81.0)	91.1 (200.9)	*Indoor clothing weighing 5 pounds for men and 3 pounds for women
207.0 (81.5)	92.2 (203.3)	*Centimeters \times 0.3937 = inches
208.3 (82.0)	93.3 (205.8)	*Pounds \times 0.4535 = kilograms

Adalimumab
M14-347 Protocol Amendment 2
EudraCT 2013-004034-15

Appendix J. 70-Day Follow-Up Phone Call – Sample

Site Name/Number: _____

Subject Number: _____

Please contact subjects who discontinue adalimumab 70 days following study drug discontinuation.

Date of Call: _____

- Lost to Follow-up (Please check this box if subject was not willing to provide any follow-up information or you were unable to speak to the subject following at least one attempt.)
- No Events Reported
- N/A subject continued adalimumab therapy after the end of their study participation

List any Adverse Events (AE) and/or Serious Adverse Events (SAE) that occurred since the subject was last seen in clinic for this study. If needed, provide AE/SAE details on the AE worksheet attached. (Please report all SAEs to AbbVie within 24 hours of being made aware of the event.)

If events are listed above, your monitor will review and retrieve the appropriate eCRF pages during their next visit.

Please fax all completed forms to:

[Name] at XXX-XXX-XXXX

Adalimumab
M14-347 Protocol Amendment 2
EudraCT 2013-004034-15

[figure not shown]

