A final phone call will be made to the subject approximately 70 days after the last dose of study drug to determine the status of any ongoing AEs/SAEs or the occurrence of any new AEs/SAEs. The 70-day follow-up phone call will not be required for any subject who initiates commercial adalimumab.

All attempts must be made to determine the date of the last dose of study drug and the primary reason for premature discontinuation. The information will be recorded on the appropriate eCRF page.

For subjects who are considered lost to follow-up, reasonable attempts must be made to obtain information on the final status of the subject. At a minimum, two phone calls must be made and one certified letter must be sent.

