6.4 Adverse Event Collection Period

All adverse events including ongoing AEs from Study M14-115, and reported from the time of study drug administration until 70 days following discontinuation of study drug administration have elapsed will be collected, whether solicited or spontaneously reported by the subject. In addition, SAEs will be collected from the time the subject signed the study-specific informed consent. Adverse event information will be collected and recorded on the appropriate eCRFs.

[figure not shown]
Subjects will be contacted approximately 70 days following study drug discontinuation for an assessment of any new or ongoing AEs, except those subjects who continue on adalimumab therapy after the end of study participation. These subjects are not required to complete the 70-day follow-up and any new AEs should be reported through the mechanism used for all post-marketing adverse experiences. The 70-day follow-up phone call will be recorded in source document only and confirmation of the contact will be faxed to AbbVie ([Appendix J](#)).

All AEs identified to AbbVie from the 70-day follow-up phone call will be collected as source data to be evaluated and reported ([Figure 3](#)). Thus, all SAEs and nonserious AEs as defined by AbbVie, reported during the 70-day follow-up phone call must be captured

in the clinical database. The end of trial is the last subject contact, i.e., the 70 day follow-up call.

Adverse event information will be collected as shown in [Figure 3](#).

Figure 3. Adverse Event Collection

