11.2.1 Treatment-Emergent Adverse Events

Treatment-emergent AEs (TEAE) are defined as events that begin or worsen either on or after the first dose of the study medication and within 70 days after the last dose of the study drug.

Events where the onset date is the same as the study drug start date are assumed to be treatment-emergent, unless the study drug start time and the adverse event start time are collected and the adverse event start time is prior to the study drug start time. If an incomplete onset date was collected for an adverse event, the event will be assumed to be treatment-emergent unless there is other evidence that confirms that the event was not treatment-emergent (e.g., the event end date was prior to the study drug start date).

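### The Appendix J form for the 70-day safety call accepts lost to follow-up after one failed attempt, below the two calls and certified letter that Protocol 5.4.1 requires

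*Protocol*

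**What the plan says.** Protocol 5.4.1 describes the last planned contact: "A final phone call will be made to the subject approximately 70 days after the last dose of study drug", to learn the status of ongoing adverse events and whether new ones have occurred. Two paragraphs later the same section turns to subjects who cannot be found. It says "For subjects who are considered lost to follow-up, reasonable attempts must be made to obtain information on the final status of the subject", and then sets the floor: "At a minimum, two phone calls must be made and one certified letter must be sent".

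Protocol 6.4 says "The 70-day follow-up phone call will be recorded in source document only" and has confirmation of the contact faxed to the sponsor, citing Appendix J. That appendix, headed as a sample, has one line for the date of the call and a lost-to-follow-up box. The box has two triggers. One is refusal: "Please check this box if subject was not willing to provide any follow-up information". The other is that the site was "unable to speak to the subject following at least one attempt". The form does not refer to 5.4.1.

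SAP 11.2.1 counts as treatment-emergent any event that begins or worsens on or after the first dose and "within 70 days after the last dose of the study drug". SAP 9.1 ends each subject's exposure 70 days after the last dose, and SAP 11.2.2.9 uses that exposure as the denominator for event rates per 100 patient-years.

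**The concern.** The two places use the same term for the same contact but ask for different effort. A site that makes one unanswered call, ticks the box and faxes the form has met the form's condition and fallen short of the body text. Nothing on the form would show this, because it has no place for a second call or a letter. A subject who answered and declined is recorded in the same way as one who was never reached.

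The call is the last scheduled contact, and it falls in a period that the analysis counts both as time at risk and as treatment-emergent. If sites stop trying early, some events in that period may go unrecorded.

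**Working it through.** **Side by side**

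| Item | Protocol 5.4.1 | Protocol Appendix J |
|---|---|---|
| Phone attempts before a subject counts as lost | at least 2 | at least 1 |
| Certified letter | 1 | not mentioned |
| Place to record each attempt | not specified | one call-date line |
| Subject reached but declines | not addressed | same box as not reached |

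Section 5.4.1 does not say whether the failed 70-day call counts as one of the two. Even if it does, one more call and a letter are still due when the form already allows the box to be ticked.

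**How much of the window depends on the call**

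Inputs: last dose at Week 38 on every-other-week dosing or Week 39 on weekly dosing, with none at Week 40 (Protocol 5.5.1); adverse events monitored at Week 40 (Protocol Table 2); Week 40 nominal day 281 (SAP Table 3); exposure ends at last dose + 70 days (SAP 9.1). With the first dose on Day 1, nominal day = 7 × week + 1.

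Every-other-week completer:
- Last dose: 7 × 38 + 1 = Day 267.
- Covered by the Week 40 visit: 281 − 267 = 14 days.
- Left to the call: 70 − 14 = 56 days.
- Counted exposure: 267 + 70 = 337 days, so 56/337 = 17%.

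Weekly completer:
- Last dose: 7 × 39 + 1 = Day 274.
- Covered by the Week 40 visit: 281 − 274 = 7 days.
- Left to the call: 70 − 7 = 63 days.
- Counted exposure: 274 + 70 = 344 days, so 63/344 = 18%.

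These are nominal figures; the ±3-day windows for visits and doses move them by a few days. For early discontinuers, 5.4.1 asks for the discontinuation visit within 2 weeks of the last dose, which leaves at least 70 − 14 = 56 days.

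**Number of subjects**

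This cannot be computed. The documents give neither a non-contact rate for the call nor the number of subjects exempt from it.

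**The case against.** The strongest reply is that the passages do not strictly collide. The form's wording is a floor, so a site that makes two calls and sends a letter satisfies both. Appendix J is only a sample, the mandatory wording is in 5.4.1, and Protocol 7.0 makes the investigator responsible for meeting all protocol requirements. All of that is correct, and it means the form does not waive 5.4.1. It does not remove the mismatch. Appendix J is the only model form the Protocol supplies for this call, 6.4 points to it, and its floor is below the mandatory one.

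It can also be said that 5.4.1 is about a subject's final status after discontinuation, while the box codes the outcome of one call. That reading is possible but weak, because the label is shared and 5.4.1 describes this same call just before it sets the minimum.

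Three stronger readings are tempting, and the documents do not support them:

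- **All 70 days of safety data depend on this call.** The Week 40 or discontinuation visit also follows the last dose and covers part of the period. Protocol 6.4 also collects spontaneously reported events.
- **A definite share of the 252 enrolled subjects is affected.** Any such count needs an assumed non-contact rate, and it would wrongly include subjects exempt through commercial adalimumab (Protocol 5.1, 5.4.1 and 6.4).
- **The form makes the rates per 100 patient-years too low.** Missed events would push them down, but part of any shortfall comes from the SAP itself. It adds 70 days of exposure for everyone, including exempt subjects, whose new events go to post-marketing reporting. Correcting the form would not cure that.

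**Conclusion.** The contradiction is real, in current text, and minor. Appendix J accepts lost to follow-up at one attempt and no letter, against a required two calls and one letter. It cannot document that the requirement was met, and it merges refusal with non-contact.

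The consequence is a possibility, not a documented loss. Where a site follows the form and not the body text, follow-up could be closed early for about 56 or 63 of the 70 post-dose days in a completer, or 17% to 18% of that subject's counted exposure. This rests on the nominal schedule and on no event from that stretch reaching the site by another route. The number of subjects, and so any effect on a summary rate, is unknown.

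**What to change.** Reconcile Appendix J with 5.4.1:

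- Have the no-contact box cite the 5.4.1 minimum, with a date line for each of two calls and for the certified letter.
- Add a separate box for subjects who were reached but declined. The two-call-and-letter rule should not be applied to them.
- State whether the failed 70-day call counts as one of the two.
- Leave the existing not-applicable box for subjects continuing adalimumab.

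This costs a few lines on a sample form. The extra contact effort is already required by 5.4.1, so it adds no new burden on paper.

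The SAP, dated 13 November 2017, describes enrolment and visits in the past tense. If follow-up is complete, the useful step is to report how many subjects were reached at 70 days, exempt, declined or not reached, and how many of the last group were closed below the 5.4.1 minimum. Because the call is recorded in source documents, this means a review of site records. The SAP's fixed 70-day addition to exposure is a separate matter.
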